5.5 Diet/Activity/Other Considerations

5.5.1 Diet

Patients should maintain a normal diet unless modifications are required to manage an AE such as diarrhea, nausea or vomiting.

5.5.2 Contraception

Pembrolizumab may have adverse effects on a fetus *in utero*. Furthermore, it is not known if pembrolizumab has transient adverse effects on the composition of sperm. Men and non-pregnant, non-breast-feeding women may be enrolled if they are willing to use 2 methods of birth control or are considered highly unlikely to conceive. Highly unlikely to conceive women are defined as: 1) surgically sterilized, or 2) postmenopausal (a woman who is ≥ 45 years of age and has not had menses for more than 1 year), or 3) not heterosexually active for the duration of the study. The two birth control methods can either be two barrier methods or a barrier method plus a hormonal method to prevent pregnancy. Patients should start using birth control from study visit 1 throughout the study period up to 120 days after the last dose of study therapy.

The following are considered adequate barrier methods of contraception: diaphragm, condom, copper intrauterine device, sponge, or spermicide. Appropriate hormonal contraceptives will include any registered and marketed contraceptive agent that contains an estrogen and/or a progestational agent (including subcutaneous, intrauterine, or intramuscular agents).

Patients should be informed that taking the study medication may involve unknown risks to the fetus (unborn baby) if pregnancy were to occur during the study. In order to participate in the study they must adhere to the contraception requirement (described above) for the duration of the study and during the follow-up period defined in section 7.2.4. If there is any question that a patient will not reliably comply with the requirements for contraception, that patient should not be entered into the study.

5.5.3 Use in Pregnancy

If a patient inadvertently becomes pregnant while on treatment with pembrolizumab, the patient will immediately be removed from the study. The site will contact the patient at least monthly and document the patient's status until the pregnancy has been completed or terminated. The site will report the outcome of the pregnancy to SARC without delay and **within 24 hours** if the outcome is a serious adverse experience (e.g., death, abortion, congenital anomaly, or other disabling or life-threatening complication to the mother or newborn). The site

investigator will make every effort to obtain permission to follow the outcome of the pregnancy and report the condition of the fetus or newborn to SARC. If a male patient impregnates his female partner the study personnel at the site must be informed immediately and the pregnancy reported to SARC and followed as described above and in Section 7.2.4.

5.5.4 Use in Nursing Women

It is unknown whether pembrolizumab is excreted in human milk. Since many

drugs are excreted in human milk, and because of the potential for serious adverse reactions in the nursing infant, patients who are breast-feeding are not eligible for enrollment.

5.6 Duration of Therapy

Treatment may continue until one of the following criteria applies:

- Patient achieves SD, PR, or CR and completes 35 cycles of treatment without unacceptable adverse event(s) (Section 6.1).
- Clinical or radiographic disease progression as defined by RECIST 1.1. Patient may be allowed to continue treatment after progression for a maximum of 35 cycles of treatment if they are deriving clinical benefit (refer to section 2.17).
- Patient decides to withdraw from the study
- General or specific changes in the patient's condition render the patient unacceptable for further treatment in the judgment of the site investigator
- Unacceptable adverse event(s) (Section 6.1)
- Need for > 2 dose delays due to toxicity
- Pregnancy in patient
- Patient is lost to follow-up.

5.6.1 Duration of Participation

Each patient will participate in the trial from the time of Informed Consent Form (ICF) is signed through final protocol-specified contact. After a screening phase for eligibility, patients will receive pembrolizumab every 3 weeks. Treatment for patients that achieve SD, a PR, or a CR can continue for a maximum of 2 years. At the discretion of the investigator, patients who have progressive disease (PD) but continue to achieve clinical benefit, may also continue on therapy for a maximum total duration of treatment of *35cycles*.

5.7 Duration of Follow Up

Patients will be followed for 30 days +/- 14 days after termination of study treatment or until death, whichever occurs first. Patients removed from study for adverse event(s) will be followed until resolution or stabilization of the adverse event.

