1.2. Secondary Objectives

- 1. To determine the safety and tolerability of pembrolizumab in this patient population
- 2. To determine the Progression-Free Survival (PFS) by RECIST 1.1 and Overall Survival (OS) in this patient population
- 3. To determine the response rate as measured by the immune-related Response Criteria (ir-RC)

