5.8 Criteria for Removal from Study

Patients will be removed from study when any of the criteria listed in Section 5.6 applies. The reason for study removal and the date the patient was removed must be documented in the eCRF including death or lost to follow up.

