10.3 OFF TREATMENT EVALUATIONS

Final visit is to be performed at the time (or within 30 days +/- 14 days of removal from the treatment). Off treatment evaluations will include:

- Physical exam: height, weight vital signs, ECOG performance status
- Serum β -HCG or urine pregnancy test for women of childbearing potential
- Relevant laboratory evaluations, including CBC with differential and comprehensive serum chemistry panel
- Urinalysis
- PT (or INR) and PTT
- EKG
- Recording of adverse events (for unresolved adverse events, patients should be monitored for 30 days following the last dose of study drug)
- Extent of disease evaluation with appropriate radiographic procedures if not performed within 30 days of the final visit
- Off treatment Biopsy collected due to progression (optional).

Follow-Up:

Patients who complete study treatment should be followed for survival every 6 months. Patient will be contacted by phone at a minimum and survival status will be collected and documented. Survival status can also be assessed via patient's medical records or via certified letter.

STUDY CALENDAR

| | Pre- Study | Wk 1 | Wk 4 | Wk 7 | Wk 10 | Wk 13 | Wk 16 | Wk 19 | Wk 22 | Wk 25 | Wk 28 | Wk 31 | Wk ^K 34+ | Off Treatment ¹ |
|--|----------------|------------------|---------|---------|---------------------|----------|----------|----------|--------------------|----------|----------|---------------|------------------------|-------------------------------|
| Study Drug Admin ^a | | Х | Х | Х | Х | Х | Х | Х | Х | Х | Х | Х | Х | |
| Informed consent | Х | | | | | | | | | | | | | |
| History/Demographics | Х | | | | | | | | | | | | | |
| Physical exam ^b | Х | Х | Х | Х | Х | Х | Х | Х | Х | Х | Х | Х | Х | Х |
| CBC with Differential ^c | X f | Х | Х | Х | Х | Х | Х | Х | Х | Х | Х | Х | Х | Х |
| Comprehensive Serum Chemistry Panel ^d | X f | х | Х | х | Х | Х | Х | Х | Х | Х | Х | Х | Х | Х |
| TSH, FT4, T3 | X f | Х | Х | Х | Х | Х | Х | Х | Х | Х | Х | Х | Х | |
| PT (or INR) and PTT | X f | Х | Х | Х | Х | Х | Х | Х | Х | Х | Х | Х | Х | Х |
| Urinalysis | X f | | | | | | | | | | | | | Х |
| Serum or urine pregnancy test ^e | X f | | | | | | | | | | | | | Х |
| EKG | X g | | | | | | | | | | | | | Х |
| Archival Tumor Samples (FFPE) (only patients from expansion) | Х | | | | | | | | | - | | | | |
| Adverse event evaluation | | Χ- | | | | | | | | | | | X | Х |
| Biopsies | Х | X ^J - | | | | | | | | | | | X ^J | Х |

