| Radiologic evaluation | X ^h | First | radiolo | ogic m | easurem | | | | ied at 8 bseque | | (± 1 w | eek) initiall | y, then | X ⁱ |
| Blood Sample Collection | X ^m | | | | l be col tion wi | | | | | | | 1 week), w | eek 32 | |
| Follow up | | | | | | | | | | | | | | X ⁿ |

a: Pembrolizumab

b: Including height, weight ,vital signs, ECOG performance status

c: WBC, Hgb, Plt, ANC, PT (or INR), PTT

d:Cr, K, Ca, ALT, AST, Alkaline phosphatase, Total bilirubin

e: Women of childbearing potential

f: Laboratory baseline evaluations are to be conducted within 14 days prior to first study drug dose

g:EKG within 30 days prior to first study drug administration

h: Scans and x-rays must be performed within 30 days prior to first study drug dose

i: Extent of disease evaluation with appropriate radiographic procedures if not performed within 30 days of the final visit. j: Mandatory biopsies will be collected pre and post treatment at week 0 and 8 and optional biopsies may be collected at cycle 12 (week 34) and at time of progression for 20 patients enrolled in the expansion cohorts of UPS and LPS.

k: Patients may continue on study drug beyond 12 cycles at discretion of study doctor. Use monthly visits as a template for every monthly evaluations as long as patient remains on study drug.

1: Off-study evaluation should be performed at the time (or within 30 days) of removal from study.

m: Blood samples will be collected pre-treatment (after eligibility is confirmed)

n: Patient will be followed for survival every 6 months via phone call at a minimum. Survival status will be documented after each call.

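### The survival follow-up rules conflict: section 5.7 closes about a month after treatment, while the Study Calendar requires six-monthly survival contact for patients off treatment

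*Combined protocol and SAP*

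**What the plan says.** Section 1.2 lists as a secondary objective: "To determine the Progression-Free Survival (PFS) by RECIST 1.1 and Overall Survival (OS) in this patient population".

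Four places bear on how long survival is collected:

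- **Section 5.7 (Duration of Follow Up):** "Patients will be followed for 30 days +/- 14 days after termination of study treatment or until death, whichever occurs first". The only extension is for patients removed for adverse events, who are followed to resolution or stabilization.
- **Section 5.8:** "Patients will be removed from study when any of the criteria listed in Section 5.6 applies". The section 5.6 list includes progression, unacceptable adverse events, withdrawal from the study and loss to follow-up. Treatment past progression is allowed where there is clinical benefit.
- **Section 10.3, under Follow-Up:** "Patients who complete study treatment should be followed for survival every 6 months". Contact is by phone at a minimum; medical records or a certified letter may also be used.
- **Study Calendar, footnote n (Off Treatment column):** "Patient will be followed for survival every 6 months via phone call at a minimum". It is not limited to patients who completed treatment.

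Neither 10.3 nor footnote n says when survival contact ends. Section 5.6.1 runs participation to a final protocol-specified contact, which is not dated. PFS has a definition (11.1.6) and an estimator (13.3). Section 13.3 lists OS without an estimator or censoring date.

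**The concern.** The section a site would consult for the length of follow-up gives a window that closes before any six-monthly survival contact could take place. It neither mentions survival nor refers to 10.3. Section 5.8 adds to the problem by describing the end of treatment as removal from the study.

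At stake is the OS estimate. Under the narrower rule, survival status would be lost about a month after treatment stops. The stop is often prompted by progression, so the patients censored would differ in prognosis from those still followed. That is informative censoring, which a product-limit curve cannot correct. With approximately 10 sites (12.1.3), different sites could also collect different data.

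**Working it through.** The plan states no OS sample size, event count or follow-up length, so there is no OS figure to reproduce. Steps 1 and 2 use the documents alone. Steps 3 to 5 need assumptions, which are marked.

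**1. Section 5.7 against footnote n.**
- 5.7 closes between 30 − 14 = 16 and 30 + 14 = 44 days after treatment.
- Six months is 365.25 / 2 = 182.6 days. Counted from treatment stop, the first contact comes 182.6 − 44 = 138.6 days after the latest close.
- Both cannot be the full follow-up rule for the same patient.

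**2. Section 10.3 against footnote n.** They share the six-monthly interval. One names completers, the other names patients off treatment generally. Neither excludes anyone, so they differ in coverage without contradicting each other.

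**3. Who remains if completing treatment means 35 cycles?**
- Dose 35 falls (35 − 1) × 21 = 714 days after dose 1, which is 102 weeks or 714 / 30.4375 = 23.46 months.
- Planning PFS rates are 20% and 40%, at 3 months in 13.3 and at 4 months in the synopsis.
- Assuming exponential PFS, the share still progression-free is s^(23.46/t).
- Highest: 0.40^(23.46/4) = 0.0046, or 0.19 of 40 patients. Lowest: 0.20^(23.46/3) = 0.0000034.
- Durable responders and treatment past progression would raise these figures, but this reading would still drop most patients.

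**4. How many deaths would the window see?** Assume exponential survival after treatment with median m months (m is not in the documents). The share of deaths falling within d days is 1 − 2^(−(d/30.4375)/m).

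| m (months) | d = 16 | d = 30 | d = 44 |
|---|---|---|---|
| 6 | 5.9% | 10.8% | 15.4% |
| 9 | 4.0% | 7.3% | 10.5% |
| 12 | 3.0% | 5.5% | 8.0% |
| 18 | 2.0% | 3.7% | 5.4% |

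**5. Can the bias be sized?** This is a simulation on assumed inputs, with 400,000 patients per scenario. OS is estimated by the product-limit method (13.3 names it for PFS only). Patients are censored 30 days after stopping, and treatment is capped at 24 months. The base grid of 16 scenarios has exponential progression with median 2 or 4 months, death before progression at 0.01 or 0.03 per month, and median survival after progression of 6, 9, 12 or 18 months. The error is estimated minus true 12-month OS.

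| Scenario | Error (percentage points) |
|---|---|
| Footnote n applied to everyone | 0 |
| All stop at progression (base grid) | about +3 to +28 |
| Half treated 4 months past progression | about +1 to +13 |
| 10% to 40% of progressors die with a 1-month median, the rest with 9, 12 or 18 months (48 scenarios) | about −5 to +19; negative in 4 |
| Progression median 4 months, death before progression 0.05 or 0.08 per month, survival after progression 12 to 24 months | about +2 to −14 |

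In the base grid 68% to 92% of patients are censored alive before month 12. The sign depends on whether stopping treatment marks out patients at higher or lower risk than those still followed, and the documents do not settle that.

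**The case against.** The best answer is that the protocol already has a survival rule, stated twice, and that 5.7 is not about survival. Section 5.7 never uses the word, and its next sentence concerns adverse events. Its window matches the final visit in 10.3: "Final visit is to be performed at the time (or within 30 days +/- 14 days of removal from the treatment". Footnote l times the equivalent visit from the other event: "Off-study evaluation should be performed at the time (or within 30 days) of removal from study". So removal from study and removal from treatment appear to be used interchangeably, and 5.8 can be read that way. Section 5.6.1 carries participation to a final contact rather than to day 30, and section 4.1 says data for secondary endpoints are captured. Nor does the verb complete reliably mean 35 cycles, since 10.2 also uses it for 12 cycles.

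Most of this stands, and it makes the benign reading the likelier one. But a site has to assemble that reading from several places, while 5.7 and 5.8 on their face say otherwise.

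A second objection also stands. The simulated errors are not evidence about this trial: every input is assumed, and the 4-month progression median exceeds the plan's own PFS target. They show only that the censoring could matter in either direction.

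**Conclusion.** The conflict is real but limited. Section 5.7, with 5.8, cannot be reconciled as written with six-monthly survival contact, and 10.3 leaves doubt about who receives that contact. If every patient off treatment is contacted under footnote n, OS is unaffected. If a site applies 5.7, or restricts contact to 35-cycle completers, survival collection ends about a month after treatment for most patients and OS is informatively censored. Ongoing adverse-event follow-up would extend contact for some. That most patients fall short of 35 cycles rests on the planning PFS rates and an exponential curve. The ORR decision rule is unaffected.

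A reader might infer three stronger claims that the documents do not support:

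- **Survival is not collected beyond a month, or data were lost.** Two passages require the contact, and nothing shows that it was missed.
- **A literal 10.3 ends survival contact soon after treatment for everyone.** It follows completers with no stated end; the loss would fall on non-completers, and only where footnote n is disregarded.
- **OS would be overstated by a known amount.** Neither the size nor the sign can be derived.

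The absence of an OS estimator and censoring date is missing detail. It biases nothing by itself.

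**What to change.** - **5.7:** state that the 30 +/- 14 day window is for the final visit and adverse-event collection, and refer to 10.3 for survival. Leave the adverse-event and serious-adverse-event follow-up in 5.7, 7.1.1.6 and 7.2.2 unchanged.
- **10.3:** extend six-monthly survival contact to patients who come off study treatment for any reason, matching footnote n.
- **5.8:** say that patients meeting a 5.6 criterion come off study treatment and stay in survival follow-up unless they withdraw consent to follow-up, are lost to follow-up or die. A blanket change to removal from treatment would be wrong, because 5.6 also lists withdrawal from the study and loss to follow-up, which are true study exits.
- **10.3 or 13.3, once:** survival contact continues until death, withdrawal of consent to follow-up, loss to follow-up or study closure, and OS is censored at the last date known alive.

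The cost is a wording amendment, plus about two phone or records checks per surviving off-treatment patient per year at any site that had used the narrower reading. No visits or scans are added.

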5.8 Criteria for Removal from Study

Patients will be removed from study when any of the criteria listed in Section 5.6 applies. The reason for study removal and the date the patient was removed must be documented in the eCRF including death or lost to follow up.

6. DOSING DELAYS/DOSE MODIFICATIONS

Dose reduction of pembrolizumab will not be permitted in individual patients.

6.1 Discontinuation of Therapy:

Therapy with pembrolizumab will be permanently discontinued for any of the following:

a. Severe or life-threatening adverse reactions, including, but not limited to, any of the following (SARC must be notified in the event of these AEs and final decision regarding treatment will be made after a discussion):

- Drug related grade 4 toxicity (non-hematologic or hematologic)
- Diarrhea with abdominal pain, fever, ileus, or peritoneal signs; increase in stool frequency (7 or more bowel movements over baseline), stool incontinence, need for intravenous hydration for more than 24 hours, gastrointestinal hemorrhage, and gastrointestinal perforation
- Aspartate aminotransferase (AST) or alanine aminotransferase (ALT) >5 times upper limit of normal. For patients with liver metastasis who entered the study with grade 2 elevation of AST/ALT, pembrolizumab will be permanently discontinued if AST/ALT increase ≥ 50% relative to baseline and lasting ≥ 1 week)
- Total serum bilirubin >3 times upper limit of normal
- Severe (i.e., CTCAE grade 3 or 4) motor or sensory neuropathy, Guillain-Barré syndrome, or myasthenia gravis or other neurologic symptoms that impact activity of daily living
- Severe immune-mediated reactions involving any other organs (e.g., nephritis, pneumonitis, pancreatitis, non-infectious myocarditis)
- Immune-mediated ocular disease that is unresponsive to topical immunosuppressive therapy
- Grade 4 infusion reaction

• Confirmed diagnosis of Stevens-Johnson Syndrome (SJS) or Toxic Epidermal Necrolysis (TEN)

b. Inability to reduce corticosteroid dose for immune-related adverse reactions to ≤ 10 mg prednisone or equivalent per day

c. New or worsening ophthalmologic disorders, including loss of visual acuity or visual field and evidence of retinopathy.

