 - Insulin replacement therapy is recommended for Type I diabetes mellitus and for Grade 3-4 hyperglycemia associated with

metabolic acidosis or ketonuria.

• Evaluate patients with serum glucose and a metabolic panel, urine ketones, glycosylated hemoglobin, and C-peptide.

Hypophysitis:

- For **Grade 2** events, treat with corticosteroids (1-2 mg/kg/day prednisone or equivalent). When symptoms improve to Grade 1 or less, steroid taper should be started and continued over no less than 4 weeks. Replacement of appropriate hormones may be required as the steroid dose is tapered.
- For **Grade 3-4** events, treat with an initial dose of IV corticosteroids followed by oral corticosteroids. When symptoms improve to Grade 1 or less, steroid taper should be started and continued over no less than 4 weeks. Replacement of appropriate hormones may be required as the steroid dose is tapered.

Hyperthyroidism or Hypothyroidism:

Thyroid disorders can occur at any time during treatment. Monitor patients for changes in thyroid function (at the start of treatment, periodically during treatment, and as indicated based on clinical evaluation) and for clinical signs and symptoms of thyroid disorders.

- Grade 2 hyperthyroidism events (and Grade 2-4 hypothyroidism):
 - In hyperthyroidism, non-selective beta-blockers (e.g. propranolol) are suggested as initial therapy.
 - In hypothyroidism, thyroid hormone replacement therapy, with levothyroxine or liothyronine, is indicated per standard of care.
- Grade 3-4 hyperthyroidism
 - Treat with an initial dose of IV corticosteroid followed by oral corticosteroids (1-2 mg/kg/day prednisone or equivalent). When symptoms improve to Grade 1 or less, steroid taper should be started and continued over no less than 4 weeks. Replacement of appropriate hormones may be required as the steroid dose is tapered.
 - Permanently discontinue pembrolizumab for **Grade 4** hyperthyroidism.

Hepatic Adverse Events:

- For **Grade 2** events, monitor liver function tests more frequently until returned to baseline values (consider weekly).
 - Treat with IV or oral corticosteroids (0.5-1 mg/kg/day prednisone or equivalent)
- For Grade 3-4 events, treat with intravenous corticosteroids for 24 to

48 hours (1-2 mg/kg/day prednisone or equivalent. If grade 3-4 hepatitis persists for more than 3-5 days, then begin mycophenolate 1 g twice daily. Permanently discontinue pembrolizumab for AST or ALT > 5x ULN or total bilirubin >3x ULN.

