| AST / ALT elevation or Increased | Grade 2 | Withhold | Administer corticosteroids (initial dose of 0.5- 1 mg/kg prednisone or equivalent) followed by taper | • Monitor with liver function tests (consider |
| bilirubin | Grade 3 or 4 | Permanently discontinue | • Administer corticosteroids (initial dose of 1-2 mg/kg prednisone or equivalent) followed by taper | weekly or more frequently until liver enzyme value returned to baseline or is stable |
| Type 1 diabetes mellitus (T1DM) or Hyperglycemia | Newly onset T1DM or Grade 3 or 4 hyperglycemia associated with evidence of β-cell failure | Withhold | Initiate insulin replacement therapy for participants with T1DM Administer anti-hyperglycemic in participants with hyperglycemia | • Monitor participants for hyperglycemia or other signs and symptoms of diabetes. |
| Hypophysitis | Grade 2 | Withhold | | • Monitor for signs and symptoms of |

| Immune-related AEs | Toxicity grade or conditions (CTCAEv4.0) | Action taken to pembrolizumab | irAE management with corticosteroid and/or other therapies | Monitor and follow- up |
|-----------------------------|--|--|---|--|
| | Grade 3 or 4 | Withhold or permanently discontinue ¹ | Administer corticosteroids and initiate hormonal replacements as clinically indicated. | hypophysitis (including hypopituitarism and adrenal insufficiency) |
| Hyperthyroidism | Grade 2 | Continue | • Treat with non-selective beta- blockers (eg, propranolol) or thionamides as appropriate | Monitor for signs and symptoms of thyroid |
| | Grade 3 or 4 | Withhold or permanently discontinue ¹ | | disorders. |
| Hypothyroidism | Grade 2-4 | Continue | • Initiate thyroid replacement hormones (eg, levothyroxine or liothyroinine) per standard of care | Monitor for signs and symptoms of thyroid disorders. |
| Nephritis and Renal | Grade 2 | Withhold | Administer corticosteroids (prednisone 1-2 mg/kg or | • Monitor changes of renal function |
| dysfunction | Grade 3 or 4 | Permanently discontinue | equivalent) followed by taper. | |
| Myocarditis | Grade 1 or 2 | Withhold | Based on severity of AE administer corticosteroids | • Ensure adequate evaluation to |
| | Grade 3 or 4 | Permanently discontinue | | confirm etiology and/or exclude other causes |
| All other immune-related | Intolerable/ persistent Grade 2 | Withhold | • Based on type and severity of AE administer corticosteroids | • Ensure adequate evaluation to |

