| AEs | Grade 3 Grade 4 or recurrent Grade 3 | Withhold or discontinue based on the type of event. Events that require discontinuation include and not limited to: Gullain-Barre Syndrome, encephalitis Permanently discontinue | | confirm etiology and/or exclude other causes |

NOTE:

For participants with Grade 3 or 4 immune-related endocrinopathy where withhold of pembrolizumab is required, pembrolizumab may be resumed when AE resolves to \leq Grade 2 and is controlled with hormonal replacement therapy or achieved metabolic control (in case of T1DM).

Guidelines for Infusion Reactions

Dose modification and toxicity management of infusion-reactions related to pembrolizumab

Pembrolizumab may cause severe or life threatening infusion-reactions including severe hypersensitivity or anaphylaxis. Signs and symptoms usually develop during or shortly after drug infusion and generally resolve completely within 24 hours of completion of infusion. Dose modification and toxicity management guidelines on pembrolizumab associated infusion reaction are provided in Table 5.

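### Section 6.1 makes every drug-related grade 4 toxicity a permanent stop with no endocrine exception, but Table 4 continues pembrolizumab for grade 4 hypothyroidism (1 of 10 rows), and two other endocrine rows are not aligned

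*Combined protocol and SAP*

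**What the plan says.** Section 6.1(a) gives a list of severe reactions for which pembrolizumab is permanently discontinued. One bullet reads "Drug related grade 4 toxicity (non-hematologic or hematologic". The lead-in requires notice to SARC and adds that the "final decision regarding treatment will be made after a discussion". No endocrine event is excepted. Section 5.6 ends treatment for adverse events by reference to section 6.1, and section 5.8 removes a patient from study once a section 5.6 criterion is met.

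Table 4, in section 6.2, assigns actions by event and grade. Its endocrine rows read:

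- Hypothyroidism: "Hypothyroidism | Grade 2-4 | Continue".
- Diabetes: "Newly onset T1DM or Grade 3 or 4 hyperglycemia associated with evidence of β-cell failure | Withhold".
- Hypophysitis and hyperthyroidism: "Grade 3 or 4 | Withhold or permanently discontinue".

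The NOTE below the table says: "For participants with Grade 3 or 4 immune-related endocrinopathy where withhold of pembrolizumab is required, pembrolizumab may be resumed when AE resolves to" grade 2 or less under hormone replacement or, for type 1 diabetes (T1DM), metabolic control.

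Section 5.4.2.1 covers treatment of the same events. For low thyroid function: "In hypothyroidism, thyroid hormone replacement therapy, with levothyroxine or liothyronine, is indicated per standard of care". For diabetes: "Insulin replacement therapy is recommended for Type I diabetes mellitus and for Grade 3-4 hyperglycemia", in the latter case when acidosis or ketonuria is present. Neither entry says what to do with study drug. For grade 4 hyperthyroidism the same section does say: pembrolizumab is stopped for good.

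**The concern.** A site with a patient who develops drug-related grade 4 hypothyroidism finds two instructions. Through sections 5.6, 6.1 and 5.8, the patient is put forward for permanent discontinuation and removal from study. Through Table 4, the patient takes replacement hormone and keeps receiving pembrolizumab. Nothing states which text prevails. About 10 sites are planned (section 12.1.3), so similar patients could be handled differently. One could lose treatment because of an event managed with hormone tablets; another could be dosed where the discontinuation section says stop. Dose reduction is not permitted (section 6), so the choice between continuing, withholding and stopping is the main dosing lever.

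**Working it through.** No plan figure needs reproducing. The check compares texts, using one test for every row of Table 4: at grade 4, is there an action that satisfies both the table and the section 6.1 bullet? The event is taken to be attributed to pembrolizumab, since the bullet covers only drug-related toxicity.

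| Table 4 row | Table 4 action at grade 4 | Against the 6.1 stop |
|---|---|---|
| Pneumonitis | Stop | Same |
| Diarrhea/colitis | Stop | Same |
| AST/ALT/bilirubin | Stop | Same |
| Nephritis/renal | Stop | Same |
| Myocarditis | Stop | Same |
| All other immune-related | Stop | Same |
| Hypophysitis | Withhold or stop | Stopping satisfies both |
| Hyperthyroidism | Withhold or stop | Stopping satisfies both |
| T1DM/hyperglycemia | Withhold; may resume (NOTE) | Different action named; withholding and never resuming satisfies both |
| Hypothyroidism | Continue | Nothing satisfies both defaults |

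Count: 6 same + 2 satisfied by stopping + 1 satisfied by never resuming + 1 irreconcilable = 10 rows. The direct contradiction is 1/10. A stop is not mandatory in Table 4 for 2 + 1 + 1 = 4 rows, all endocrine.

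**Does another section settle it?**

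- Section 5.4.2.1 is silent on study drug for hypothyroidism and for T1DM/hyperglycemia. For grade 4 hyperthyroidism it agrees with section 6.1, so Table 4 is the one text that still allows withholding there.
- Section 6.2(a) takes the section 6.1 events out of the general withholding rule. That ranks 6.1 above the general rule, but does not address a table entry that says to continue.

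**Does section 6.2 itself agree with Table 4?** Not fully.

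- 6.2(a) withholds for clinically significant drug-related toxicity of grade 2 or higher, while Table 4 continues for hypothyroidism at grades 2 and 3.
- 6.2(c) resumes at grade 1 or less, while the NOTE permits grade 2 or less when the endocrinopathy is controlled.

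An exception written only into section 6.1 would leave both mismatches in place.

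**The case against.** The strongest reply is that section 6.1(a) is not an automatic stop. SARC is told and a decision follows discussion, and Table 4 is titled as guidelines, so SARC could decide to continue drug on replacement hormone. This stands in part: it gives a route to a sensible outcome and lowers the severity. But section 6.1 starts from a permanent stop and Table 4 from uninterrupted dosing, and nothing says which starting point the discussion should favor.

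A reader might infer that T1DM/hyperglycemia is a second direct contradiction. The documents do not support that. Table 4 says to withhold, and resumption is permitted rather than required, so never resuming meets both texts. It is a mismatch in the named action.

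A reader might also infer that the ungraded diarrhea bullet in section 6.1 reaches below grade 4 and so conflicts with the grade 2–3 withholding in Table 4, because grade 4 already has its own bullet. But section 6.1 also lists grade 4 infusion reactions separately, which the general bullet already covers when drug-related. The list is redundant elsewhere, so redundancy proves nothing about diarrhea. Assigning a grade to the stool counts would also need CTCAE definitions that the protocol does not reproduce.

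Finally, the hypophysitis and hyperthyroidism entries carry a footnote marker, and only an unnumbered NOTE is visible in the text available. A missing footnote might say who chooses between withholding and stopping. Those rows are therefore not counted as contradictions. The hyperthyroidism point rests on the explicit grade 4 stop in section 5.4.2.1.

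**Conclusion.** The inconsistency is real and narrow. One of 10 Table 4 rows, hypothyroidism at grade 4, cannot be followed together with section 6.1. T1DM/hyperglycemia names a different action but can be reconciled. Hyperthyroidism at grade 4 is looser in Table 4 than in the two other sections.

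This rests on the current wording, on attribution to pembrolizumab, and on the absence of any statement that one text overrides the other. The documents give no frequency for these events, so the number of patients affected cannot be estimated. The response rule in section 13.1 (8 or more responders among 40, one-sided type I error 4.2%, power 82%) does not depend on which dosing instruction is followed. Severity is minor.

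**What to change.** (a) In the grade 4 bullet of section 6.1, add two exceptions, with SARC still notified each time: hypothyroidism controlled on hormone replacement (continue), and T1DM/hyperglycemia with β-cell failure (withhold, then resume once controlled as in the Table 4 NOTE).

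(b) In 6.2(a) and 6.2(c), add the matching exception, so that grade 2–3 hypothyroidism is not withheld and a controlled endocrinopathy may resume at grade 2 or less.

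(c) Split the grade 3–4 hyperthyroidism entry in Table 4: grade 3 as now, grade 4 a permanent stop, matching sections 5.4.2.1 and 6.1.

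A general sentence ranking one text over the others is not needed: the mismatches are few enough to name, and a global ranking would alter rules that are not in question here. Section 5.6 can stay, because it points to section 6.1, where the exceptions would sit.

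Cost: protocol wording in sections 6.1 and 6.2 and Table 4, plus a site memo. Sample size, visits and data collection do not change.
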